#### Preliminary Safety and Efficacy Data for Use of Omegaven™ in Other Diseases

Omegaven™ has been used for over 10 years as an adjunct to conventional fat emulsions. According to current data, an increase in the proportion of omega-3 fatty acids is thought to optimize nutrition in general, but in particular benefit patients whose underlying disease might benefit from an increase in omega-3 fatty acids. An adequate intake of omega-3 fatty acids results in anti-inflammatory and immunomodulatory effects that are protective in nature from inflammatory tissue damage, capillary permeability, and improved immunological resistance. It may also reduce the risk of thrombosis and increase microvascular perfusion due to its anti-aggregatory and vasodilatory effects.

In Europe and Asia, the use of parenteral omega-3 fatty acids has been used in the following adult patient populations (24-28):

- post traumatic and post surgical patients
- patients experiencing early stages of sepsis/SIRS
- patients at risk of hyperinflammatory processes
- patients with inflammatory bowel disease (Crohn's disease, ulcerative colitis)
- patients with inflammatory skin diseases (psoriasis, atopic eczema)

The dosing used in these patients was 0.1 g (1ml) to a maximum of 0.2 (2ml) /kg body weight. The infusion rate used did not exceed 0.5ml/kg/body weight/hour. Since it was intended to be infused in combination with conventional fat emulsions, the total fat intake was limited to 10-20% as fish oil. The duration of administration did not exceed 4 weeks.

#### Preliminary Safety and Efficacy Data for Use of Omegaven™ in Infants

Pediatric experience with Omegaven™ is limited to 2 unpublished clinical trials. These trials were performed in Germany and Taiwan (29). The German study was a controlled, randomized, open parallel-group clinical study to investigate whether or not omega-3 fatty acids could be incorporated into the plasma phospholipids of very low birth weight preterm infants. In this 7-day safety trial, Omegaven™ use was evaluated on the basis of clinical, laboratory, and antioxidant parameters and lipid metabolism. Treatment was started on day 3-5 of life and continued for a total of 7 days. Patients received Omegaven™ plus conventional soybean fat emulsion or soybean emulsion alone. The maximum dose of Omegaven™ in the study was 0.2 gm/kg/day. The study concluded that the Omegaven™ was well tolerated in this group of preterm infants in respect to both hematological and biochemical parameters. The incidence of reported adverse events between both study groups was similar. The eicosapentaenoic acid (EPA) content of plasma phospholipids increased significantly in the Omegaven™ arm, with the proportion of EPA to the total fatty acids reaching almost three times the baseline value. The sum of omega-3 fatty acids showed a significantly greater increase in the Omegaven™ group compared to the conventional treatment arm.

The Taiwanese study was a single center, controlled, open-labeled study conducted to investigate the safety of parenteral administration of Omegaven™ in preterm infants. The group of 20 infants were randomized to one of two treatment groups; one consisting of Omegaven™/conventional lipids and the other consisting of conventional lipids alone. The average dose of Omegaven™ in the treatment group of this 14-day study was 0.13 + 0.02 g/kg/day. There were no significant differences between the two groups with regard to body weight and length. Similarly, there was no significant difference in the

hematological or biochemical parameters. There were no adverse events that were attributable to Omegaven use. It was concluded that Omegaven™ was well tolerated in these preterm infants.

## 4.0 Inclusion/Exclusion Criteria

### Inclusion Criteria:

1. Patients aged 0 to 2 years will be PN dependent (unable to meet nutritional needs solely by enteral nutrition) and are expected to require PN for at least another 30 days
2. Patients considered eligible for study participation must have parenteral nutrition associated liver disease (PNALD) as defined as a direct bilirubin of >2.5 mg/dl or more. Other causes of liver disease should be excluded. A liver biopsy is not necessary for treatment.
3. Signed patient informed consent.

4. The patient must have utilized standard therapies to prevent the progression of his/her liver disease including surgical treatment, cyclic PN, avoiding overfeeding, reduction/removal of copper and manganese from PN, advancement of enteral feeding, and the use of ursodiol (i.e., Actigall®).

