#### Exclusion Criteria:

1. Other causes of chronic liver disease (Hepatitis C, Cystic fibrosis, biliary atresia, and alpha 1 anti-trypsin deficiency,)
2. Enrollment in any other clinical trial involving an investigational agent (unless approved by the designated physicians on the multidisciplinary team)
- 3.. The parent or guardian or child unwilling to provide consent or assent
4. Patients with severe hemorrhagic disorders
5. Patients with severe liver disease not caused by prolonged PN and renal insufficiency
6. Patients with uncontrolled diabetes mellitus

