## Details of Omegaven™ Administration

After baseline labs are obtained (Table 2 and 3), therapy with Omegaven™ will be initiated at the goal dose of 1 gram /kg/day and is infused over 12-24 hours. Omegaven™ will be infused intravenously through either a central or peripheral catheter alone or in conjunction with parenteral nutrition. If additional fat calories are needed, they will be provided via the enteral route.. The same standards of care provided to all patients receiving parenteral nutrition solution will be followed. Routine nutritional monitoring is described in Table 3.

Table 2: Suggested Schedule Safety Monitoring for Omegaven™ Therapy

(To be done baseline pre-Omegaven™ therapy and weekly until direct bilirubin <0.4 mg/dL)

Parameter	Baseline	Biweekly	Monthly
Essential Fatty Acid Profile	X		X
PT	X	X	
PTT	X	X	
INR	X	X	

Table 3: Suggested Monitoring Schedule for Omegaven™ Therapy  
(Amended December 26, 2006)

Parameter	Baseline (pre- Omegav- en)	Dail y	Q week * -	Periodicall y**
Weight	X	X		
Fluid balance	X	X		
Vital Signs	X	X		
Catheter site/function	X	X		
Laboratory test:				
Sodium	X		X	
Potassium	X		X	
Chloride	X		X	
Glucose	X		X	
BUN	X		X	
Creatinine	X		X	
Triglycerides	X		X	
Calcium	X		X	
Magnesium	X		X	
Phosphorus	X		X	
Prealbumin	X		X	
C reactive protein	X		X	
Albumin	X		X	
Total protein	X		X	
SGPT	X		X	
Alkaline phosphatase	X		X	
Bilirubin (total and direct)	X		X	

GGT	X		X	
AST	X		X	
Copper				X
Iron				X
Vitamins A,D,E				X
Essential Fatty Acid Profile	X		X	
Free cholesterol	X		X	
Free fatty acids	X		X	
Lipid Panel	X		X	
Hemoglobin	X		X	
Hematocrit	X		X	
RBC	X		X	
WBC	X		X	
Platelets	X		X	
PT	X		X	
PTT	X		X	
INR	X		X	
Fibrinogen				
Selenium				X
Zinc				X
Carnitine				X
Aluminum				X
Retinol binding protein (check when getting Vit A)				X

\* More often as necessitated by clinical course; may be reduced in patients who are stable and whose biochemical markers have improved. Refer to protocol for additional information

In the event that a patient is unable to achieve adequate calories parenterally and is unable to tolerate enteral feeds, it may be necessary to evaluate whether or not the patient should continue the study with Omegaven™ as monotherapy or resume therapy with conventional fat emulsions so that additional parenteral fat calories can be given. The clinical team, in conjunction with the patient's primary physician, will determine if the patient should be removed from the protocol. The DSMB will also be notified.

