### ***Analysis of Efficacy of Omegaven™***

The primary outcome to gain preliminary evidence of efficacy will be based on the time from baseline to normalization of bilirubin level, i.e, first time point among three consecutive in which bilirubin is  $< 2\text{ mg/dL}$ . We do not anticipate that any subject will present a rebound on direct bilirubin after normalization. However, we will describe the cohort with respect to the frequency of rebounds in bilirubin levels.

Crude comparisons of time to normalize direct bilirubin levels using Omegaven™ Results of these analysis will be compared with results of analysis excluding subjects who die or are transplanted. Time to reach a total bilirubin of 1.2 will also be compared using survival analysis methods. Analysis of this outcome will proceed as described for direct bilirubin.

We will also describe individual profiles over time (i.e., 2 months before baseline or birth until end of follow-up period) for all subjects using graphical methods. Trends in liver function markers over time will be explored using generalized linear models in which correlations of observations within subjects will be accounted using a generalized equations or random effects approach. In these models we will hypothesize that for both groups biochemical levels increase for all tests with equal slope before treatment. After treatment, however, levels should be decreasing for patients in the Omegaven™ group. We will perform these analyses including only subjects who did not die or undergo transplantation and including all subjects but assigning for subjects who died or underwent a transplant their worse possible outcome after they died or had the transplant. Using descriptive statistics, we will also explore the association between spikes in blood tests over time and predictors including transfusions of red blood cell products and blood stream infections.

Assessment of efficacy will be also based on comparison of means (or medians) of the mean and maximum modified PELD scores of each subject across all follow-up weeks. Adjustments of these comparisons for potential confounders will be based on linear regression models. Mean rates of infection will be compared. Liver transplant, mortality, and red blood cell product transfusion events will be collected.

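### Entry needs only one direct bilirubin above 2.5 mg/dL, so some infants enrolled at a temporary peak can reach the normalisation endpoint without a drug effect

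*Combined protocol and SAP*

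**What the plan says.** Section 4.0, inclusion item 2, sets the bilirubin criterion as "parenteral nutrition associated liver disease (PNALD) as defined as a direct bilirubin of >2.5 mg/dl or more". It names no repeat test, interval or duration.

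The other entry conditions are:
- "Other causes of liver disease should be excluded", with no method given and biopsy not required;
- infants "are expected to require PN for at least another 30 days";
- "The patient must have utilized standard therapies to prevent the progression of his/her liver disease", with no minimum duration and no bilirubin re-check afterwards.

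The listed exclusions cover "Other causes of chronic liver disease (Hepatitis C, Cystic fibrosis, biliary atresia, and alpha 1 anti-trypsin deficiency" and several other conditions. Current infection and recent transfusion are not among them.

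Section 6.0 starts therapy "After baseline labs are obtained", and Table 3 includes total and direct bilirubin at baseline and weekly. No interval is set between the qualifying value and the baseline value.

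Section 10.0, Analysis of Efficacy, runs the primary outcome from baseline to the "first time point among three consecutive in which bilirubin is" below 2 mg/dL. The same section plans a descriptive look at the association between "spikes in blood tests over time and predictors including transfusions of red blood cell products and blood stream infections". It also plans individual profiles from two months before baseline (or from birth).

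**The concern.** Selecting infants because a fluctuating marker is above a cut-off selects some who are briefly above their usual level. Later values fall back towards that level whatever the treatment. Here the success threshold lies only 0.5 mg/dL below the entry threshold, so the fall can be enough to count as success.

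Requiring three consecutive low values guards against one chance low reading at the end. It does nothing about one chance high reading at the start: an infant whose usual level is below 2 will supply three low values once the peak has passed.

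The study is non-randomised and open-label. Unaided recoveries would be read as drug effect in any single-group or before-and-after reading, and the time to normalisation would look shorter than it should.

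**Working it through.** **Inputs from the documents.** Entry: direct bilirubin > 2.5 mg/dL. Success: three consecutive values < 2 mg/dL, taken here as direct bilirubin because the following sentences of Section 10.0 speak of direct bilirubin. Testing: weekly (Table 3). The gap is 2.5 − 2 = 0.5 mg/dL, or 0.5/2.5 = 20% of the entry value. The documents give no bilirubin variance, spike frequency or spike duration, so the plan has no figure to reproduce. Everything below is an assumption shown as a range.

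**Step 1: one spike.** Let an infant with usual level b peak at p, with the excess halving every h weeks. The time to fall below 2 is h × log2[(p − b)/(2 − b)].
- b = 1.0, p = 3, h = 0.5: 0.5 × log2(2.0/1.0) = 0.5 weeks
- b = 1.5, p = 3, h = 1: 1 × log2(1.5/0.5) = 1.6 weeks
- b = 1.8, p = 4, h = 2: 2 × log2(2.2/0.2) = 6.9 weeks

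So a spike can satisfy the endpoint within about 0.5 to 7 weeks with no treatment.

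**Step 2: share of enrolled infants, no drug effect.** Weekly value = exp(log M + 0.4z + s + σe), where:
- M is the median usual level among screened infants;
- z and e are standard normal (between infants, and week to week);
- σ is 0.15 or 0.30;
- s is either zero, or rises by log 1.8 with probability 10% per week and halves every 1 or 2 weeks.

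The infant enters at the first qualifying value in nine weekly screens. The endpoint is three consecutive values < 2 within 12 weeks of entry. Ranges run over the six combinations of σ and spike setting.

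| M (mg/dL) | Single value > 2.5 | Two consecutive weekly values > 2.5 |
|---|---|---|
| 1.5 | 18% to 54% | 3% to 32% |
| 2.0 | 11% to 34% | 2% to 19% |
| 3.0 | 4% to 13% | 1% to 6% |
| 4.0 | 1% to 4% | 0% to 2% |

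Spikes are not essential. At M = 1.5 and σ = 0.30 with no spikes at all, the single-value share is 51%.

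**Step 3: does a second value help?** This depends on how long a spike lasts. A second model used M = 1.6, log-SD 0.5 between infants, 15% within-infant variation, additive spikes of 1 to 3 mg/dL at 5% per week, and 13 weeks of follow-up. Two separate implementations gave:

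| Spike duration | Single value → confirmed (run A) | Single value → confirmed (run B) |
|---|---|---|
| Gone within a week | 49% → 8% | 61% → 12% |
| Half-life 1 week | 46% → 32% | 58% → 43% |
| Half-life 2 weeks | 41% → 36% | 52% → 46% |

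The levels differ with modelling detail; the pattern does not. In run A the relative reduction is (49 − 8)/49 = 84% for the shortest spikes, (46 − 32)/46 = 30% at a one-week half-life and (41 − 36)/41 = 12% at two weeks.

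**The case against.** **The entry process is more than one number.** Infants must have other causes of liver disease excluded, must already have used standard therapies and must be expected to need PN for 30 more days. Section 5.0 adds an individual assessment of suitability. This stands as mitigation: it should lower the number of transient cases. None of it requires a sustained elevation.

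**The models hold the usual level flat.** Section 10.0 hypothesises rising levels before treatment, and Section 1.0 says abnormalities worsen with time on PN. In a rerun of the second model, adding a 3% to 5% weekly rise cut 49% to between 26% and 16%. This stands, and is one more reason not to treat the upper figures as estimates.

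**The comparison may be partly protected.** A reader might infer that the comparison with soybean emulsion is biased in favour of Omegaven. The documents do not show that. Hypothesis 2.1 starts both groups after bilirubin exceeds 2.5, so regression to the mean would act in both. The cancellation depends on how the soybean group is assembled and indexed, which the available text does not say.

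**The plan does not predict transient bilirubin spikes.** A reader might infer that it does. It says only that it will explore associations between spikes in blood tests and certain predictors. Likewise, reliance on one value is inferred from the absence of a confirmation rule.

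**Conclusion.** The concern holds as a gap in the analysis plan. Nothing requires the qualifying bilirubin to be sustained, the endpoint does not correct for that, and Section 10.0 describes only crude comparisons of time to normalisation. Some infants can therefore meet the endpoint without a drug effect.

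The size is unknown. Under the assumed models it is a few per cent if screened infants typically sit near 4 mg/dL, and up to about 50% to 60% if they typically sit near 1.6 mg/dL with frequent spikes. The upper end needs a typical level below the success threshold and no upward drift, so it is not a forecast for this trial.

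A reader might also infer that a confirmatory value would all but remove the problem. That is true only if spikes vanish within about a week, and the documents give no spike duration. With longer spikes the reduction is modest. Nor is it enough to compare the qualifying value with the Table 3 baseline, since nothing prevents the two from being the same sample or a day apart.

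The change is worth making because it is cheap, with low confidence about how much it will matter.

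**What to change.** Leave eligibility, treatment and testing as they are. Add to Section 10.0:

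1. The time-to-normalisation clock starts at the pre-Omegaven baseline direct bilirubin in Table 3. Report how many infants are already at or below 2.5 at that point.
2. The primary comparison of time to normalisation is adjusted for baseline direct bilirubin.
3. A pre-specified sensitivity analysis repeats the primary result in infants with the baseline value and at least one earlier value both above 2.5. The earlier value must come from a different date, a stated minimum interval before baseline, and can be taken from the two-month profile already planned.
4. Soybean infants are indexed and selected by the same rule. They have no Omegaven start date, so the text must say how their index date is assigned.

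The cost is a few sentences and no extra tests. The downside is precision: the confirmed subset held 34% to 88% of infants in one set of simulations and 52% to 89% in another. Section 7.0 mentions 13 infants in the study at the time of writing. On that number, 34% is 0.34 × 13 ≈ 4 infants and 89% is 0.89 × 13 ≈ 12. The restricted result should therefore be labelled as supporting. Baseline adjustment helps only the between-group comparison, and neither step removes the bias fully.

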## 5.0 Enrollment/Randomization

NICU attendings will screen their patients for infants who need prolonged parenteral nutrition (TPN) and have Parenteral Nutrition Associated Liver Disease. The attending physician will ask the family if they would like more information about the study. [name] will be notified of these infants, and assess if they are suitable candidates. [name] or the NICU research nurses will explain the study to the infant's parents / legal guardians and obtain informed consent in the NICU at Vanderbilt Children's Hospital.

Assessment of the effect of treatment will be based on a non-randomized, open-labeled, prospective study of intravenously administered Omegaven™ fat emulsion to determine safety and preliminary efficacy in the treatment of PN associated liver injury.

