#### Potential Risks of No Treatment

Since Omegaven™ will only be offered to those patients for whom no standard therapy is likely to be safe and effective, the risks of not being treated are those allowing for the natural history of their disease and associated clinical manifestations to progress. These include fulminate liver failure and death.

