#### Summary – Overall Risk Assessment

Patients will be at some risk inherent in taking a pharmaceutical agent that has not been fully evaluated for long duration treatment. However, the availability of safety data demonstrates no life-threatening risks or toxicities to vital organs or physiologic functions. Prolonged bleeding times and inhibition of platelet aggregation are a potential risk, especially to those patients with an underlying coagulopathy or those being treated with an anticoagulant. The potential benefits of Omegaven™ in this patient population are mainly based on the experimental evidence and a single case of dramatic success. However, the study will only be available to those for whom no standard therapy is available or appropriate, or has already failed. The risks and potential benefits will require careful individual assessment by both the investigators and patients. The heterogeneity of clinical manifestations will lead to non-uniform risk-benefit ratios across the eligible patient population.

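### Inclusion item 4 asks only for prior use of standard therapies, so it does not ensure the narrower population Section 7.0 describes, and infants already improving at baseline can count as Omegaven successes

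*Combined protocol and SAP*

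**What the plan says.** **Entry.** Section 4.0, inclusion item 4: "The patient must have utilized standard therapies to prevent the progression of his/her liver disease". The list that follows names surgery, cyclic PN, avoidance of overfeeding, trace-element reduction, "advancement of enteral feeding, and the use of ursodiol". Item 2 requires liver disease "as defined as a direct bilirubin of >2.5 mg/dl or more". Neither item asks for a minimum time on therapy, a failed response, a stable regimen, a repeat bilirubin value or a bilirubin trend. The exclusion criteria and Section 5.0 add no such condition.

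**Population used to justify the risk.** Section 7.0, Potential Risks of No Treatment: "Omegaven™ will only be offered to those patients for whom no standard therapy is likely to be safe and effective". Section 7.0, Summary – Overall Risk Assessment: "the study will only be available to those for whom no standard therapy is available or appropriate, or has already failed".

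**Design and outcome.** Section 5.0 describes a "non-randomized, open-labeled, prospective study of intravenously administered Omegaven™ fat emulsion to determine safety and preliminary efficacy". Section 10.0, Analysis of Efficacy: "The primary outcome to gain preliminary evidence of efficacy will be based on the time from baseline to normalization of bilirubin level". Normalization is the first of three consecutive values below 2 mg/dL.

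**Related analyses.** Section 10.0 also plans graphs of each infant's course from 2 months before baseline (or from birth), and models of liver-marker trends before and after treatment. Adjustment for confounders is mentioned only after the PELD score comparison, and no confounder is named.

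**The concern.** Having used a therapy is not the same as having failed it. An infant who began ursodiol or cyclic PN shortly before entry, with a response still to come, can satisfy item 4 without fitting either statement in Section 7.0. Two things are at stake.

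- **The risk-benefit argument.** Section 7.0 justifies an agent without long-term evaluation by describing infants with no workable alternative. If the entry criteria admit others, that argument does not describe everyone who may be treated.
- **Attribution.** The clock for the primary outcome starts at baseline and stops at normalization, whatever produced it. With no randomized control, a bilirubin that was already on its way down at baseline is recorded as a response on Omegaven.

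**Working it through.** The plan states no sample size, event rate or power for this outcome, so there is no figure to reproduce. The check compares the passages.

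**1. Do the three population statements agree?**

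| Place | Condition on standard therapy |
|---|---|
| Section 4.0, inclusion item 4 | Has been used |
| Section 7.0, Potential Risks of No Treatment | Unlikely to be safe and effective |
| Section 7.0, Overall Risk Assessment | Unavailable, unsuitable, or has failed |

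The first can be met without the second or third. Item 2 does not close the gap: it shows that the infant is cholestatic at entry, not that the bilirubin is stable or rising despite therapy.

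**2. Can an infant who is already improving become a success?** The entry threshold is above 2.5 mg/dL and the success threshold is below 2 mg/dL. For an infant who enters just over the threshold, the fall needed is a little more than 2.5 − 2 = 0.5 mg/dL. A pre-existing decline that continues past baseline would meet this. Requiring three consecutive values guards against a stray low reading, but says nothing about cause.

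**3. Does anything in the primary analysis separate the causes?**

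- Confounder adjustment is attached to the PELD comparison. For time to normalization, Section 10.0 refers only to crude comparisons, in a sentence that breaks off.
- The rule that counts the Omegaven period from 30 days after its start stands under the safety analysis. The efficacy time runs from baseline.
- The trend models hypothesize that markers rise with equal slope in both groups before treatment. An infant already improving departs from that hypothesis, and no entry criterion keeps such an infant out.
- The limitations paragraph names misclassification by direct bilirubin, not concurrent therapy.

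**4. Do the documents treat standard therapies as inert?** No. Section 1.0 rates them as at most moderately successful and credits partial enteral nutrition with protection against developing the disease. Section 7.0 calls the available therapies frequently inadequate. Some response is possible, but a large one is not implied.

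**5. Can the size be computed?** No. It would need the share of infants whose bilirubin was falling at baseline and the share of those who would have normalized anyway. The documents give neither.

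**The case against.** **Item 4 is being read too literally.** It is in the past tense and lists several measures together, so it is unlikely that a whole list was begun just before entry. Section 5.0 has each infant assessed for suitability, and the Section 7.0 statements can be read as a further limit on enrollment. This has force: the mismatch does not prove that a different population is being enrolled. But the suitability assessment has no stated criterion on this point, and one recently started therapy is enough to raise the question.

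**The plan already looks at the pre-baseline course.** This is correct. Individual profiles and trend models would show an infant who was improving before entry, so such infants would not go unseen. They would still count in the primary result, because nothing carries the profile into that analysis.

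**A comparison group would share the effect.** Hypothesis 2.1 names infants on conventional fat emulsions, and they could receive the same therapies. If timing were alike in both groups, much of the effect would cancel. The text available for review gives no entry rule or source for that group, so similar timing can be neither assumed nor ruled out.

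**The study claims only preliminary efficacy.** This lowers the stakes, but Hypothesis 2.1 is still a claim of faster resolution, and that claim needs attribution.

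**Conclusion.** The inconsistency between Section 4.0 and Section 7.0 is established by the text. The attribution problem is established as a possibility: infants already improving at baseline can count as Omegaven successes, and the primary analysis has no means of setting them apart. The size is unknown and could be near zero.

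A reader might infer three stronger things that the documents do not support.

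- **That therapies had just been started in the enrolled infants.** Nothing says so. The rule permits it, and that is all.
- **That the result is biased in favour of Omegaven.** Against a conventional-emulsion group, the direction depends on whether therapy timing differs between groups, and the documents do not say.
- **That a number of false responders can be estimated.** Any such figure would rest on invented shares. The 13 infants mentioned in Section 7.0 are those in the study when that text was written, not a planned sample size. A count of responders would also not measure bias in a time-to-event outcome.

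The point is worth acting on because the remedy is cheap. It does not undermine the study as a source of preliminary evidence.

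**What to change.** 1. **Reconcile the text.** Inclusion item 4 and the two statements in Section 7.0 should describe one population. Which description is right is for the sponsor to decide.
2. **Abstract start dates** of the discrete standard therapies (ursodiol, cyclic PN, trace-element reduction, surgery) from the medical record for every infant analysed, including any conventional-emulsion group, and tabulate them relative to baseline. Section 6.0 already draws study data from medical records. The case report form is not among the documents, so some dates may already be captured.
3. **Add one sensitivity analysis to Section 10.0.** Using the pre-baseline profiles already planned, repeat the primary analysis in infants whose direct bilirubin was not falling before baseline, and show it beside the main result. Fix the rule for *not falling* before the analysis is run and apply it identically in any comparison group. Report infants with too few earlier values to classify as a separate line.
4. **Do not require feeding to be unchanged.** Feed advancement is gradual by nature, so such a condition would leave few infants or select those who cannot advance.

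**Cost.** Some chart abstraction, one table, one repeated analysis and a wording change, with no change to patient care. The subset will be smaller and its estimate less precise, and very young infants will have limited pre-baseline data. The analysis also does not address feed advancement or other changes after baseline.
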